2.1.4.2 Adverse events variables

Adverse event observation period

- The pre-treatment period is defined as the time between the date of signing of the informed consent and the first injection of IMP,
- The on-treatment period is defined as the time from the first injection of IMP up to and including 3 days after the last injection of IMP (treatment-emergent AE [TEAE] period),
- The post-treatment period is defined as the time starting 4 days after last injection of IMP (after the TEAE period).

All adverse events (including SAE, AESI) will be coded to a lower-level term (LLT), preferred term (PT), high-level term (HLT), high-level group term (HLGT), and associated primary system organ class (SOC) using the version of Medical Dictionary for Regulatory Activities (MedDRA) currently in effect at Sanofi at the time of database lock.

The occurrence of adverse events (including SAE and AESI) will be recorded from the time of signed informed consent until the end of the study or the resolution/stabilization of all SAE and AESI.

An adverse event of special interest (AESI) is an AE (serious or non-serious) of scientific and medical concern specific to the Sponsor’s product or program, for which ongoing monitoring and immediate notification by the Investigator to the Sponsor is required. Such events may require further investigation in order to characterize and understand them

AESI are listed below:

- ALT >3 x ULN;
- Serious allergic/hypersensitivity reactions;
- Pregnancy occurring in a female patient administered IMP/NIMP;
- Symptomatic overdose of IMP/NIMP

Table 3 - Criteria for AESI

AE Grouping	Criteria
AESI	
Serious allergic/hypersensitivity reactions	eCRF form “Hypersensitivity/Allergic”
Pregnancy	eCRF form “Pregnancy”
Symptomatic overdose	“Overdose of IMP” or “Overdose of NIMP” checked and “Symptomatic overdose” checked in eCRF form “Overdose”
ALT increase > 3X ULN	eCRF form “ALT increase”

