- All treatment-emergent serious adverse events by primary SOC, HLGT, HLT, and PT, showing the number (%) of patients with at least 1 serious treatment-emergent adverse event, sorted by the internationally agreed SOC order. The other levels (HLGT, HLT, PT) will be presented in alphabetical order
- All treatment-emergent serious adverse events regardless of relationship and related to IMP, by primary SOC, HLGT, HLT, and PT, showing the number (%) of patients with at least 1 treatment-emergent serious adverse event, sorted by the internationally agreed SOC order. The other levels (HLGT, HLT, PT) will be presented in alphabetical order

Analysis of all treatment-emergent adverse event(s) leading to treatment discontinuation

- All treatment-emergent adverse events leading to treatment discontinuation, by primary SOC, HLGT, HLT, and PT, showing the number (%) of patients sorted by the internationally agreed SOC order. The other levels (HLGT, HLT, PT) will be presented in alphabetical order

Analysis of adverse events of special interest

- Serious allergic/hypersensitivity reactions, pregnancy and overdose for the combined on-treatment and post-treatment period will be included in overall AE summaries if any are reported. ALT increase $>3 \times$ ULN for the TEAE period is included in laboratory PCSA summary and listed in the PCSA listing which will include both the on-treatment and post-treatment periods.

Gastrointestinal adverse events

- The number (%) of patients with events reported on the AE form for gastrointestinal adverse events will be summarized by PT for each treatment group.

Analysis of pre-treatment and post-treatment adverse events

- All pre-treatment adverse events by primary SOC and PT, showing the number (%) of patients with at least 1 pre-treatment adverse event, sorted by the internationally agreed SOC order and decreasing incidence of PTs within each SOC in the Soliqua 100/33 group
- All posttreatment adverse events by primary SOC and PT, showing the number (%) of patients with at least 1 posttreatment adverse event, sorted by the internationally agreed SOC order and decreasing incidence of PTs within each SOC in the Soliqua 100/33 group

Listings

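### The ALT >3 x ULN event of special interest is found by an eCRF form in Table 3 but reported from laboratory data in Section 2.4.5.2, over a different period and denominator

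*SAP*

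**What the plan says.** SAP Section 2.1.4.2 lists four AESIs: ALT above 3 x ULN, serious allergic or hypersensitivity reactions, pregnancy, and symptomatic overdose. Table 3 in the same section gives the criterion for finding each.

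- **ALT.** The criterion is "eCRF form “ALT increase". No laboratory value enters the rule.
- **Allergic reactions.** The row is labelled "Serious allergic/hypersensitivity reactions", and its criterion is "eCRF form “Hypersensitivity/Allergic", with nothing further.
- **Overdose.** The criterion needs the form and ticked boxes, including "Symptomatic overdose” checked in eCRF form “Overdose".

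Section 2.4.5.2 then says where the AESIs are reported. ALT above 3 x "ULN for the TEAE period is included in laboratory PCSA summary and listed in the PCSA listing"; only the listing extends to the post-treatment period. The other three are described as "Serious allergic/hypersensitivity reactions, pregnancy and overdose for the combined on-treatment and post-treatment period" and go into the overall AE summaries. Table 2 (Section 1.6) records, as a change made in response to regulatory comments, that AEs and AESIs are summarized over on-treatment and post-treatment time together.

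**The concern.** An AESI needs one rule that decides who is a case, over what period, and out of how many patients. For ALT the SAP gives two rules that do not agree: an investigator-completed form, and a laboratory threshold applied to whatever test results qualify for the PCSA tables. Nothing says how the two relate or which one prevails.

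With 120 patients planned per arm (Section 1.3), one patient is 1/120 = 0.83 percentage points. If such events are few, the choice of rule could decide whether an arm shows any ALT cases at this threshold. The SAP singles these events out for immediate notification, and this version states that their summary was revised after regulatory comments, so the by-arm count should be unambiguous.

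**Working it through.** The SAP gives no event figure to reproduce, so the check sets its rules for the ALT AESI side by side.

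| | Form route | Laboratory route |
|---|---|---|
| Source | 'ALT increase' form (Table 3) | Laboratory PCSA data (2.4.5.2) |
| Threshold in the output | None: AE tables go by MedDRA term | >3 x ULN |
| Local results | No condition stated | Used only if a local normal range is supplied (2.5.3) |
| Denominator | Safety population of the arm (2.4.5.2) | Patients assessed for the parameter in the TEAE period (2.4.5, 2.4.5.4) |
| Period | AE tables cover on-treatment and post-treatment time | Summary: TEAE period. Listing: both periods |

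**Period.** Table 2 promises AESI summaries over the whole on-study period. Section 2.4.5.2 confines the ALT summary to the TEAE period, so a post-treatment case would be listed but not tabulated. The liver paragraph of 2.4.5.4 does mention PCSA proportions at any post-baseline visit. It does not say whether post-treatment values count, and the common rule in 2.4.5 restricts PCSAs to the TEAE period. Either way that table uses laboratory data only.

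**How many patients would be assessed.** In the flow chart (Appendix C), the serum chemistry row carries a single mark, which reads as screening Visit 1. The layout comes from PDF text, so this needs confirming against the original table. If it is right, no on-treatment ALT is scheduled. On-treatment values would then come mainly from unscheduled or local tests, which is where the normal-range condition applies. The patients tested would be selected, probably because something prompted the test.

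**Illustration.** Assume 2 cases in one arm, a safety population of 120 (the planned arm size), and k patients in that arm with a usable on-treatment ALT.

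- Safety-population denominator: 2/120 = 1.7%.
- PCSA denominator, k = 5: 2/5 = 40%.
- PCSA denominator, k = 10: 2/10 = 20%.
- PCSA denominator, k = 120: 2/120 = 1.7%.
- PCSA table when neither result has a usable range: 0 cases.

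The same two patients can therefore appear as anything from 0 to 40%. The number of cases and k are assumptions; the SAP gives neither.

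**Allergic row.** Section 2.1.4.2 says an AESI "is an AE (serious or non-serious) of scientific and medical concern", so AESI status does not itself establish seriousness. Table 3 adds a ticked qualifier for overdose but none for allergic reactions. Whether that matters depends on which reactions the form is completed for, and the SAP does not say.

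**Overdose.** The list and Table 3 require symptoms; Section 2.4.5.2 omits the word.

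**The case against.** **On ALT.** An AESI is by definition an AE, and all AEs are coded and tabulated. A case on the form therefore reaches the AE tables on the safety-population denominator whatever happens in the PCSA table. That stands, and a reader who inferred that such a case vanishes from by-arm reporting would be wrong. The AE tables, however, carry no 3 x ULN threshold, so they do not give the count of this AESI. The combined on-study AE table is by system organ class only, and the preferred-term tables are split into treatment-emergent and post-treatment.

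It can also be said that 3 x ULN cannot be judged without a ULN, so requiring a range is inherent in the definition. That is fair for the laboratory rule. It does not help where the investigator judged the result against a local report but the range did not reach the database. How often that would happen is unknown.

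**On allergic reactions.** A reader might infer that Table 3 counts non-serious reactions as serious. The SAP does not support that as a fact. The eCRF is not shown, and if the form is completed only for serious reactions, Table 3 and the list agree. Section 2.4.5.2 also sends these events to the overall AE summaries and describes no table by AESI category, so no specified output shows a separate count that the missing condition would inflate. What stands is that Table 3 leaves the condition unstated.

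**On overdose.** The sentence sits under the AESI heading, and Section 2.4.3.2 already treats overdose cases as AEs or SAEs. This is a wording inconsistency and no more.

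**Conclusion.** The ALT point holds. Table 3 and Section 2.4.5.2 identify the same AESI from different sources, and the resulting summaries have different denominators and periods. The period in 2.4.5.2 also conflicts with Table 2. A form-reported or post-treatment case can be absent from the by-arm laboratory summary at the 3 x ULN threshold while still appearing by preferred term in the AE tables. PCSA percentages may rest on few, selectively tested patients. The size cannot be fixed from the SAP: under the assumptions above, two cases could be shown as anything from 0 to 40%, against 1.7% of a full arm. The practical weight depends on the flow chart scheduling no on-treatment serum chemistry, which is how the extracted table reads.

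The allergic and overdose points are secondary clarifications. Mislabelling of allergic reactions would arise only if the form also captures non-serious ones. None of this touches the efficacy summaries. The ALT rule should be settled before database lock.

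**What to change.** 1. In Table 3, define the ALT AESI once: an 'ALT increase' form or a laboratory ALT above 3 x ULN.
2. In Section 2.4.5.2, report it by arm over the safety population, on-treatment plus post-treatment, counting each patient once. This also brings the section into line with Table 2. Keep the laboratory PCSA table alongside, with the number of patients assessed shown.
3. In the allergic row of Table 3, add that the linked AE must be recorded as serious, or state that the form is completed only for serious reactions.
4. In Section 2.4.5.2, write symptomatic overdose.

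The cost is SAP wording and a few lines of programming. AE seriousness (a listed item in 2.4.5.2) and both ALT sources are already in the planned data. The one real task is reconciling ALT forms with laboratory records.

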2.1.4.3 Deaths

The deaths observation period are per the observation periods defined above.

- Death on-study: deaths occurring during the on-study observation period
- Death on-treatment: deaths occurring during the treatment-emergent adverse event period
- Death post-study: deaths occurring after the end of the study

2.1.4.4 Laboratory safety variables

Clinical laboratory data consists of blood analysis, including hematology, clinical chemistry, and urinalysis. Clinical laboratory values will be summarized in both standard international units and conventional units when applicable.

Blood samples for clinical laboratories will be taken at designated visits (see study flowchart in [Appendix C](#)). The following laboratory data will be measured at a central laboratory:

- Hematology: erythrocytes, hemoglobin, hematocrit, leukocytes and platelets.
- Clinical chemistry: AST, ALT, ALP, total bilirubin (if >ULN, then the direct and indirect sub-fractions must be measured), creatinine, uric acid, sodium, potassium

Urine samples will be collected at designated visits (see study flowchart in [Appendix C](#)). Urinalysis tests will include pH, glucose, ketones, leukocytes, blood/hemoglobin, and protein.

Technical formulas are described in [Section 2.5.1](#).

2.1.4.5 Vital signs variables

Vital signs include: height, weight, BMI, heart rate (HR), systolic and diastolic blood pressure, (see study flowchart in [Appendix C](#) for designated visits). They will be performed after the patient has been seated for at least 5 minutes. Blood pressure and HR will be assessed 3 times with at least 1 minute between each measurement following the 5-minute rest period. The mean of the 3 measurements will be analyzed for each vital sign variable (HR, SBP, and DBP).

2.1.5 Pharmacokinetic variables

N/A.

2.1.6 Pharmacodynamic/genomics endpoints

N/A.

2.1.7 Quality-of-life endpoints

The schedule of the following quality of life endpoints are specified in the study flowchart in [Appendix C](#). The sample questionnaires can be found in the study protocol.

- TRIM-D;
- Patient and Physician Global Treatment Effectiveness Evaluation Scales.

2.1.7.1 Treatment Related Impact Measure – Diabetes

The general treatment-related impact on patients' health related quality of life, treatment satisfaction and treatment behavior will be assessed using the TRIM-D questionnaire according to the study schedules.

The TRIM-D questionnaire is a 28-item measure with 5 domains assessing Treatment Burden, Daily Life, Diabetes Management, Compliance and Psychological Health. This PRO measure can be scored independently for each domain or as a total score (1).

The 5-point Likert like response options, for all items, range from (1) Not at all satisfied/convenient, Never to Extremely/Almost always, Always or Extremely dissatisfied/inconvenient to (5) Extremely satisfied/convenient, depending upon the item stem and are scored on a scale of 0 to 100 so that a higher score indicates a better health state (less negative impact).

The TRIM-D variables include TRIM-D scores (total and domain scores) and the change in TRIM-D scores from baseline to endpoint.

A domain score is calculated if a respondent answers at least half of the items in a multi-item domain (or half plus 1 in the case of domains with an odd number of items).

2.1.7.2 Patient and Physician Global Treatment Effectiveness Evaluation Scales

Patient- and physician-rated global treatment effectiveness evaluation scales are instruments that will be measuring whether patient's overall response to treatment is excellent, good, moderate, poor, or whether the patient's condition is worsening. The variables related to these patient-rated and physician-rated global treatment effectiveness scales include the response to the question "Overall, how effective has the treatment been in controlling your diabetes, since the start of study medication?" at Week 26. Physician-rated global treatment effectiveness evaluation will be collected in eCRF, and patient-rated global treatment effectiveness evaluation will be collected in the hand-held electronic device.

2.1.8 Health economic endpoints

N/A.

2.2 DISPOSITION OF PATIENTS

This section describes patient disposition for both patient study status and the patient analysis populations.

Screened patients are defined as all patients who signed the informed consent.

Randomized patients consist of all patients with a signed informed consent form who have had a treatment kit number allocated and recorded in the IRT database, regardless of whether the treatment kit was used or not.

For patient study status, the total number of patients in each of the following categories will be presented in the clinical study report using a flowchart diagram or summary tables:

- Screened patients
- Screen failure patients and reasons for screen failure
- Nonrandomized but treated patients
- Randomized patients
- Randomized but not treated patients
- Randomized and treated patients
- Patients who have completed the study treatment as scheduled
- Patients who discontinued the study treatment, and the reasons for study discontinuation
- All patients who attended the Week 26 visit, regardless of whether they discontinued IMP during the 26-week treatment period;
- Patients who attended the Week 26 visit and had discontinued IMP during the 26-week treatment period.
- Patients who have completed the study/ follow up as scheduled
- Patients who discontinued the study /follow up, and the reasons for study discontinuation
- Status at last study contact

For screened, screen failure, and nonrandomized but treated patients, percentages will be calculated using the number of screened patients as the denominator. All other categories of patients will be presented by treatment group and the percentages will be calculated using the number of randomized patients within each treatment group as the denominator. Reasons for treatment discontinuation will be supplied in tables giving numbers and percentages by treatment group.

A summary of the distribution of patients by region and ethnicity/race will also be provided (overall number of patients screened, randomized, and treated, as well as number of patients randomized, discontinued from study treatment, and discontinued from study for each treatment group).

Patients treated but not randomized, patients randomized but not treated, and patients randomized but not treated as randomized will be identified and described in separate listings. The patients that are randomized and not treated as randomized will be part of efficacy and safety analyses. Patients randomized but not treated will be included in efficacy analysis. Safety data of patients treated but not randomized will be reported separately.

All important deviations including randomization and drug-dispensing irregularities will be summarized in tables giving numbers and percentages of deviations by randomized treatment group.

Additionally, the analysis populations for safety and efficacy will be summarized in a table by number of patients in the randomized population.

- Efficacy population: intent-to-treat (ITT) population
- Safety population

2.3 ANALYSIS POPULATIONS

Patients treated without being randomized will not be considered randomized and will not be included in any efficacy population.

Patients who are dispensed study drug without calling the IRT or before calling the IRT are considered nonrandomized patients. They are excluded from any population for analysis, including safety. However, if these patients experienced any significant safety event, they would be documented separately in the clinical study report.

The randomized population includes any patient who has been allocated to a randomized treatment regardless of whether the treatment kit was used.

For any patient randomized more than once, only the data associated with the first randomization will be used in any analysis population. The safety experience associated with any later randomization will be assessed separately.

The safety experience of patients treated and not randomized will be reported separately, and these patients will not be in the safety population.

2.3.1 Efficacy populations

Efficacy analyses will be based on the ITT population, defined as all randomized patients. Patients will be analyzed for efficacy analyses according to the treatment group to which they are allocated by the IRT according to the randomization schedule at the randomization visit (as randomized), irrespective of the treatment actually received.

2.3.2 Safety population

Safety analyses will be based on the safety population, defined as all randomized patients who received at least 1 dose of open-label IMP, regardless of the amount of treatment administered. Patients will be analyzed for safety analyses according to the treatment actually received.

In addition:

- Nonrandomized but treated patients will not be part of the safety population, but their safety data will be presented separately.
- Randomized patients for whom it is unclear whether they took the IMP will be included in the safety population as randomized.
- When a patient is exposed to different IMPs, the patient will be analyzed for safety in the treatment group (Soliqua 100/33 or Lantus) in which he/she was treated the longest.
- Patients will be excluded from the safety population only if there is documented evidence (i.e., all study dates recorded as no medication taken) that patients have not taken IMP.

2.4 STATISTICAL METHODS

Due to early termination of the trial with limited sample size, analyses described in this section will only be performed if sufficient data is available.

2.4.1 Demographics and baseline characteristics

In general, descriptive statistics of quantitative efficacy and safety endpoints (result and change from baseline) by scheduled visit will be provided on observed cases (OC), i.e., only including patients having a non-missing assessment at a specific visit.

Continuous data will be summarized using the number of available data, mean, standard deviation (SD), median, minimum, and maximum for each treatment group. Categorical and ordinal data will be summarized using the number and percentage of patients in each treatment group.

Parameters will be summarized on the randomized population analyzed in the treatment group to which they were randomized. Summaries for the safety population will be included in the appendices if the size of the safety population is different (>10%) from the size of that in the primary analysis population for any treatment group.

Parameters described in [Section 2.1.1](#) will be summarized by treatment group and overall (pooled across treatment groups) using descriptive statistics.

P-values on the treatment difference for the demographic and baseline characteristic data will not be calculated.

In general, no specific description of the safety parameters will be provided at baseline. If relevant, the baseline values will be described along with each safety/efficacy analysis.

2.4.2 Prior or concomitant medications

The concomitant and posttreatment medications will be presented in the randomized population for each treatment group using counts and percentages. No statistical test for the between-group difference will be performed.

Medications will be summarized by treatment group according to the WHO-DD dictionary, considering the first digit of the anatomical therapeutic chemical (ATC) class (anatomic category) and the first 3 digits of the ATC class (therapeutic category). A given medication may be classified in more than 1 ATC class. All ATC codes corresponding to a medication will be summarized, and a patient will be counted once in each ATC category (anatomic or therapeutic) linked to the medication. Therefore a patient may be counted several times for the same medication.

Concomitant and post-treatment medications will be presented by anatomic and therapeutic categories and sorted by decreasing frequency of ATC based on the incidence in the Soliqua 100/33 group. In case of equal frequency regarding ATCs (anatomic or therapeutic categories), alphabetical order will be used.

Prior, concomitant and posttreatment antidiabetic medications classified as antidiabetic insulin therapy and antidiabetic non-insulin therapy will be presented separately.

- The antidiabetic insulin therapy will be summarized by pre-defined classification of
 - Basal insulin
 - Short-acting insulin
 - Pre-mixed insulinand standardized medication name.
- The antidiabetic non-insulin therapy will be summarized by pre-defined classification of
 - Biguanides
 - Sulfonylurea
 - Glinides
 - Thiazolidinedione
 - DPP-4 inhibitors
 - SGLT-2 inhibitors
 - GLP1-RA
 - Alpha-glucosidase inhibitors
 - Other

and standardized medication name.

